6.3 Sample size calculation

The current feasibility study will aim to recruit 40 patients. No formal sample size is feasible or appropriate, but this number is sufficient to allow identification of barriers to recruitment and retention (the latter informing the likely drop-out rate for the future phase 3 trial) and the duration and design of the exercise therapy intervention.

The primary objective of the future phase 3 trial will be to determine whether exercise therapy results in a clinically meaningful improvement in HRQOL at 16 weeks post-randomisation. Assuming a mean population score of 60 (SD 20) based on QoL scores previously reported in other mesothelioma studies, we currently estimate that a sample size of 84 patients in each arm is required to detect a 10-point improvement in EORTC QLQ C30 quality of life scores, with 90% power at 5% two-sided significance level. With a currently assumed 25% drop-out rate, based on the ‘Prehab4Cancer’ dropout rate in patients with NSCLC, we estimate that we would require a total sample size of 224 patients. Data from the current feasibility study will (a) provide a more robust estimate of baseline mean HRQOL score (based on the population score recorded from all patients at baseline assessment), (b) allow a more precise estimate of drop-out rate based on an optimised exercise intervention and (c) allow us to calculate the number of centres needed based on the recruitment rate achieved.

6.4 Co-enrolment guidelines

Patients may not be entered into any other clinical trial that aims to deploy an exercise programme for the duration of their participation within the study. Access to trials of systemic anti-cancer therapies, radiotherapy or surgery is permitted.

6.5 Withdrawal of patients from the study

Patients will be withdrawn from the study if any of the following occur:

- Patient withdrawal of consent
- Clinical opinion of the doctor that the patient should withdraw

If a patient moves to another area during the trial follow-up period, efforts will be made to complete follow-up in conjunction with the new primary physician / team or general practitioner.

7 BASELINE ASSESSMENT

Having provided written or witnessed verbal informed consent to participate in the study, participants will all undergo the same baseline assessment. This will include recording of:

- Patient demographics, disease characteristics, including subtype and stage, co-morbidities and medication history (including current or prior systemic anti-cancer therapy).
- Routine blood results, including full blood count (FBC), C-reactive protein (CRP) and albumin
- Body Mass Index (BMI) and malnutrition universal screening tool (MUST) score
- Functional fitness measurements in the form of:
 - Hand grip strength
 - 6 minute walk distance (6MWD)
 - 30 second sit-to-stand (STS) test
- Patient related outcome measures (PROMs) via completion of the following questionnaires related to HRQoL, wellbeing and symptoms:
 - Euroquol quality of life survey (EQ-5D-5L)
 - 36-item short form survey (SF-36)
 - European organisation for research and treatment of cancer (EORTC) QLQ-C30
 - Hospital Anxiety and Depression Scale (HADS)
 - Short Warwick Edinburgh Mental Wellbeing Scale ((S)WEMWBS)
- Presence/absence of features of sarcopenia utilising:
 - Strength, assistance with walking, rising from a chair, climbing stairs, and falls (SARC-F) screening questionnaire

- Skeletal muscle area and visceral fat index measurements on routinely-acquired clinical CT scan within the preceding 3 months

8 RANDOMISATION

Randomisation should occur immediately after baseline assessment has been completed. Eligible participants will be randomly allocated using an online system (sealed envelope) to either 'Standard Care' or 'Exercise Therapy' in a 1:1 ratio using random permuted blocks. Randomisation will be performed using an online system (sealedenvelope.com).

9 POST-RANDOMISATION

9.1 Standard Care Arm

Participants randomised to Standard Care will undergo routine clinical follow-up. Refer to schedule of assessments. Relevant clinical updates, including hospital admissions and any treatment updates (e.g. commencement or discontinuation of SACT) will be recorded at 8, 16 and 26 weeks post-randomisation. Participants will complete the questionnaires as per the above PROMs performed at their baseline assessment visit at 8, 16 and 26 weeks post-randomisation. If required, questionnaires can be posted out to patients and returned to the study team using a pre-paid addressed envelope. Study members can assist participants with completion of these questionnaires remotely if required. A study visit will be arranged at week 16 post randomisation to repeat functional fitness measurements as detailed above. Wherever possible, this study visit will be co-ordinated with the patient's routine clinic appointment. If the patient has had any follow-up CT scans performed as part of their routine clinical care during their study follow-up period, this will be reviewed to measure total skeletal muscle area and visceral fat index. If their MUST score indicates malnourishment at baseline assessment, a referral to NHS dietetic services will be made. During the follow-up period, patients will be sign-posted to local community activities and services that are available to promote long-term health improvement. It will be made clear to participants within the standard care arm that they are free to undertake exercise or increased physical activity if they wish. Any increase in exercise activity or participation in local generic community exercise programmes will be recorded at follow-up visits.

9.2 Exercise Therapy (Intervention) Arm

Participants randomised to the Exercise Therapy arm will undergo an individualised assessment by either a physiotherapist or a qualified exercise professional with specialist cancer training, either in hospital or in the community. Refer to schedule of assessments. Following this initial assessment, patients will receive a personalised exercise, wellbeing and nutritional support package. The exercise programme will incorporate 3 sessions per week. One session per week will be supported by the physiotherapist or qualified exercise professional and the other 2 sessions will be independent sessions done in the participant's own home or local health club/gym if available. The total duration of the programme is 12 weeks. The exercise programme will incorporate both cardiovascular and resistance training, and will be progressive throughout the duration of the programme. The exercise programme will be tailored to take into account the participant's current level of fitness and familiarity/confidence with exercise, available equipment and injuries. Participants will be given a diary to record completion of each exercise session. If their MUST score indicates malnourishment at baseline assessment, a referral to NHS dietetic services will be made.

Relevant clinical updates, including hospital admissions and any treatment updates (e.g. commencement or discontinuation of SACT) will be recorded at 8, 16 and 26 weeks post-randomisation. Participants will complete the questionnaires as per the above PROMs performed at their baseline assessment visit at 8, 16 and 26 weeks post-randomisation. If required, questionnaires can be posted out to patients and returned to the study team using a pre-paid addressed envelope. Study members can assist participants with completion of these questionnaires remotely if required. A study visit will be arranged at week 16 post randomisation to repeat functional fitness measurements as detailed above. Wherever possible, this study visit will be co-ordinated with the patient's routine clinic appointment. If the patient has had any follow-up CT scans performed as part of their routine clinical care during their study follow-up period, this will be reviewed to measure total skeletal muscle area and visceral fat index. During the follow-up period, patients will be sign-posted to local community activities and services that are available to promote long-term health improvement.

Any clinical concerns arising during the exercise programme will be highlighted to the patient's clinical team via the mesothelioma CNS.

9.3 Semi-structured Interviews

Up to five patients who were deemed as potentially eligible at screening, read the patient information sheet but decline to participate will be invited to participate in a semi-structured interview to explore their reasons for declining to participate, in order to determine barriers to recruitment.

A further 10 – 20 study participants, including participants who drop-out of the study before completion and those who complete the study, will be invited to a semi-structured interview to examine their views on the randomisation process, the exercise therapy intervention, study outcome measures (including the functional fitness assessments and questionnaires) and follow-up, in order to determine barriers to study retention and inform design of the phase 3 study.

Interviews can be conducted in person, ideally co-ordinated with a routine clinic appointment, or remotely. Audio recordings will be transcribed and anonymised audio transcriptions will be reviewed for qualitative analysis at the University of Surrey.

9.4 Schedule of Assessments

Visit	Pre-screening	Baseline	Week 1 (+/- 7 days)	Week 8 (+/- 2 wks)	Week 16 (+/- 3 wks)	Week 26 (+/- 4 wks)
Routine Clinical Activity						
Mesothelioma MDT review	X					
Outpatient clinic review		X				
Contrast CT thorax	X					X
Routine clinical follow-up				X	X	X
Study Activity						
Review eligibility criteria		X				
If eligible, introduce study and provide PIS		X				
Informed written consent		X				
Study registration		X				
Record baseline data		X				
Complete HRQoL questionnaires ¹		X				
Functional fitness assessment ²		X				
SARC-F screening questionnaire		X				
Review recent [#] CT for total skeletal muscle area and visceral fat index		X				
Record BMI + MUST score		X				
Randomisation		X				
Remote qualitative Interview (optional)					X	X*
Post-randomisation standard of care arm						
Record relevant clinical and/or physical activity updates				X	X	X
Complete HRQoL/wellbeing questionnaires ¹				X	X	X
Functional fitness assessment ²					X	
Review follow-up CT for total skeletal muscle area and visceral fat index						X
Post-randomisation intervention arm						
Record relevant clinical updates				X	X	X
Physiotherapist/exercise professional assessment			X			
Commence 12 week exercise programme			X			
Complete HRQoL/wellbeing questionnaires ¹				X	X	X
Review exercise session attendance and exercise compliance				X	X	X
Functional fitness assessment ²					X	
Review follow-up CT for total skeletal muscle area and visceral fat index						X
Record adverse events				X	X	

¹EQ-5D, SF-36, HADS, (S)WEBWMS and EORTC QLQ-C30 questionnaires, can be returned by post if no F2F routine clinical visit scheduled

²30 seconds sit-to-stand test, 6 minute walk test and hand grip strength

[#]Within preceding 3 months

*If not previously done

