3 STUDY FLOWCHART

4 SUMMARY OF STUDY

4.1 Plain English Summary

Malignant pleural mesothelioma (MPM) is an aggressive, strongly associated with asbestos exposure. It most frequently affects the lining of the lung (pleura), but can also affect the other parts of the body, including the lining of the heart and abdomen. The incidence of MPM has been increasing over the last decade, despite legislative control of industrial asbestos use, due to a long latency period between initial exposure and development of the disease, and is predicted to continue to increase over the next 5 – 10 years.

Patients with MPM often experience troublesome symptoms including breathlessness, pain and fatigue. They can also experience anxiety and depression and feel like their quality of life is worse than before they were diagnosed. Sarcopaenia is a complex condition, where there is an interplay between inflammation and cancer, which ultimately results in low skeletal muscle mass.

Malnutrition and sarcopaenia is common in individuals with MPM, and is associated with worse outcomes, including in those who get chemotherapy.

Unfortunately, the average life expectancy following a diagnosis of mesothelioma is approximately 12 months. Currently, treatment in patients who are fit enough is aimed at prolonging this life expectancy, and involves drug treatment in the form of either chemotherapy or more recently immunotherapy. Whether a person with mesothelioma receive this treatment can depend on their physical fitness.

Exercise Therapy

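### Interviews with drop-outs are planned to find barriers to retention, but the schedule times them only at week 16 or 26 and nothing links an interview to the time of drop-out

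*Combined protocol and SAP*

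**What the plan says.** Section 9.3 states who is to be interviewed: "A further 10 – 20 study participants, including participants who drop-out of the study before completion and those who complete the study, will be invited". The purpose is given as "in order to determine barriers to study retention and inform design of the phase 3 study". On mode it says: "Interviews can be conducted in person, ideally co-ordinated with a routine clinic appointment, or remotely". It names no week.

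The timing appears only in the section 9.4 table. The row "Remote qualitative Interview (optional" has a mark at week 16 (plus or minus 3 weeks) and a second at week 26 (plus or minus 4 weeks), footnoted "If not previously done". The table has no column for early withdrawal.

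Section 6.5 opens with "Patients will be withdrawn from the study if any of the following occur" and lists two triggers: withdrawal of consent and a doctor's opinion. It provides for follow-up of patients who move area. It does not mention an exit interview or contact after withdrawal.

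Barriers to retention are a secondary objective (section 5.2), and section 10 says the qualitative analysis will focus on facilitators of and barriers to retention. The synopsis separately lists reasons for drop-out as a secondary outcome.

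**The concern.** The people who leave early can say most directly why participants leave. A site that works from the 9.4 table has no prompt to interview such a person when they go, and the first prompt comes at week 16. Someone who leaves at week 5 would wait 8 weeks to the earliest permitted date (week 13) and 11 weeks to week 16 itself. If the week 16 contact is missed, the fallback is week 26, which is 21 weeks after they left.

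The protocol says that "the average life expectancy following a diagnosis of mesothelioma is approximately 12 months". In such a population, a wait of weeks to months can cost interviews through death, deterioration or lost contact, and it weakens recall of the decision to leave. Drop-outs will be few in a study of this size, and a missed interview may not be recoverable. The retention findings feed the phase 3 design, so thin or late evidence from drop-outs carries forward.

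**Working it through.** **The plan's own figure.** The documents give no calculation for the interviews. The only drop-out rate is the 25% in section 6.3, assumed for the phase 3 trial from a lung cancer programme. There, 84 / (1 − 0.25) = 112 per arm, or 224 in total, which matches the stated total. The 25% is therefore a proportion of those randomised. Applying it to this study is my assumption.

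**Inputs**
- Recruitment target: 40 (section 6.3). Lower bound for Green: 20 (section 13).
- Follow-up: 26 weeks. First interview slot: week 16, or week 13 at the early edge of its window (section 9.4).
- Life expectancy: about 12 months from diagnosis (section 4.1).
- Assumptions: drop-out is spread evenly over 26 weeks, and the 12 months is a median with constant hazard.

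**Number leaving before the first slot.** Expected drop-outs = 40 × 0.25 = 10.
- Before week 13: 10 × 13/26 = 5.
- Before week 16: 10 × 16/26 = 6.2.
- If drop-out were 10%, these become 2.0 and 2.5 of 4. If it were 40%, they become 8.0 and 9.8 of 16.

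**Mean wait.** With even spread, those leaving before week s wait s/2 on average: 13/2 = 6.5 weeks, or 16/2 = 8 weeks. Missing the week 16 slot adds a further 26 − 16 = 10 weeks.

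**Risk of death during the wait.** This is 1 − 0.5^(wait in months / 12), evaluated at the mean wait.
- 6.5 weeks = 1.5 months: 1 − 0.5^(1.5/12) = 8%.
- 8 weeks = 1.85 months: 1 − 0.5^(1.85/12) = 10%.
- With the hazard doubled: 16% and 19%.

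Expected deaths among early drop-outs are 5 × 0.083 = 0.4 to 6.2 × 0.101 = 0.6. With doubled hazard they are 0.8 to 1.2. Deterioration, lost contact and fading recall come on top, and the documents give no basis for a figure.

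**At 20 recruits.** Drop-outs = 20 × 0.25 = 5, of whom 2.5 to 3.1 leave before the first slot. Expected deaths in the wait are 0.2 to 0.3, or 0.4 to 0.6 with doubled hazard.

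**Mix of interviewees.** No sampling rule or minimum number is given. If interviewees mirrored a cohort of 40 with 10 drop-outs, 10 to 20 interviews would include 2.5 to 5 drop-outs. In a random draw of 10, the hypergeometric probability of no drop-out is 3.5%, and of at most two it is 51%. For a draw of 20 the figures are 0.02% and 3.2%. All of these are before any loss during the wait.

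**The case against.** The strongest reply is that nothing here stops a site from interviewing a drop-out promptly. Section 9.3 names drop-outs, allows remote interviews and sets no week. Section 9.4 calls the interview optional and remote, so no study visit is needed. Section 6.5 does not bar later contact. The table is also not a complete list of interviews: those with patients who decline the study (sections 6.2.3 and 9.3) have no entry in it either. All of this stands. A reader might infer that 9.3 and 9.4 cannot both be followed for an early drop-out, but the documents do not support that.

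A reader might also infer that the retention objective will be answered mainly by people who stayed. That does not follow from the interview weeks. The mix depends on a sampling rule that the plan does not state, and reasons for drop-out are a separate outcome not confined to interviewees. Someone who only stops exercising is not withdrawn under section 6.5 and keeps the week 8, 16 and 26 contacts in section 9.2.

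The size can be overstated too. On the same survival assumption, about 19% die by week 16 and 29% by week 26, but those risks run from time zero. The relevant risk is death between drop-out and interview. To suppose that all 3 early leavers among 5 drop-outs would be lost has no support.

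What remains is narrower: for a drop-out, the only stated timing is a late one, and neither a prompt at drop-out nor a minimum number is given. A recorded reason for leaving does not replace an interview about randomisation, the programme, the assessments and follow-up.

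**Conclusion.** The point holds as a weakness in timing and sampling. It is neither a contradiction nor a demonstrated bias towards those who stayed. Followed literally, the schedule puts about 5 to 6 of 10 drop-outs on a mean wait of 6.5 to 8 weeks, with a risk of death in that wait of about 8 to 10% and up to about 19% if their hazard is doubled. In expectation that is about one interview or fewer lost to death, plus an unquantified loss to illness, lost contact and recall.

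These figures are illustrative. They rest on a drop-out rate borrowed from the phase 3 assumption, even spread over 26 weeks, and 12 months read as a constant-hazard median. The 12 months runs from diagnosis, while section 6.2.3 sets no limit on time from diagnosis to enrolment. Performance status 0 to 2 would lower the risk, and being a drop-out would probably raise it. The change is still worth making, because drop-outs are few and interviewing them when they leave is a better method at low cost.

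**What to change.** 1. In section 9.4, add an entry at withdrawal or drop-out to the interview row. Keep weeks 16 and 26 for those still in follow-up.
2. In section 9.3, add a sentence that participants in either arm who leave the study will be invited, if they agree to be contacted, to an optional remote interview within about 2 to 3 weeks of leaving.
3. In section 9.3, reserve a stated minimum share of the 10 to 20 places for drop-outs, as far as enough of them agree, and keep places for completers. Filling places with drop-outs first would be a mistake: about 10 drop-outs could take every place at the lower bound, and 9.3 requires both groups.
4. Check that the consent form covers contact after withdrawal. It was not among the text reviewed, so this may already be in place.

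The cost is modest but not nil. Interviews would be triggered by events rather than visits, so sites must report departures promptly, and there would be slightly fewer places for completers. The interview total need not change. The protocol's section on amendments requires ethics committee and R&D approval before the revised text can be used.

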5.2 Secondary Objectives

- To determine barriers to study recruitment
- To determine barriers to study retention
- To determine safety and tolerability of the exercise intervention and study assessments

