10 STATISTICAL ANALYSIS PLAN

We will use descriptive statistics to describe the demographics and clinical characteristics of the study population. Means (with standard deviations) or medians (with inter-quartile ranges) will be used to summarise continuous variables, depending on their distribution and proportions to summarise categorical variables.

Total recruitment, recruitment rate, study drop-out rate and intervention adherence rate will be reported by simple descriptive statistics, or proportions where appropriate.

Semi-structured interviews will be analysed using Framework Analysis¹⁹, which will involve a five-step process:

1. Familiarisation with the data
2. Identifying a thematic framework
3. Indexing
4. Charting
5. Mapping and interpretation

The analysis will be predominantly deductive, as it will specifically focus on facilitators and barriers to study retention, and to the uptake and experience of the exercise intervention.

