11 END OF TRIAL

Trial recruitment will terminate either 12 months after opening or after 40 patients have been recruited, whichever is soonest. Trial participation will cease once the final patient has completed their 26-week follow-up.

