12 SAFETY REPORTING

All Adverse Events will be reported directly to the sponsor.

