12.1 Adverse Event (AE)

An adverse event is any untoward medical occurrence that the patient experiences whilst participating in the clinical trial. This includes occurrences that are not necessarily caused by or related to the trial intervention.

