12.3 SAEs Related to Study Procedures

Related SAEs will be any SAE that is reported as possibly, probably or definitely related to the prescribed exercise programme. See below for all definitions for the relationship to the protocol intervention.

Relationship	Description
Unrelated	There is no evidence of any causal relationship
Possible	There is some evidence to suggest a causal relationship (e.g. the event occurs within a reasonable time after administration of the trial intervention) However the influence of other factors may have been contributed to the event (e.g. the patient's clinical condition, other concomitant treatments)
Probable	There is evidence to suggest a causal relationship and the influence of other factors is unlikely
Definitely	There is clear evidence to suggest a causal relationship and other possible contributing factors can be ruled out

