12.4 Adverse Event Recording and Reporting

All AEs must be recorded on the patient's medical records. AEs must be recorded as they are reported during the visit. Full details of AEs including the nature of the event, start and stop dates, severity, relationship to study intervention and outcome must be recorded. AEs must be followed until resolution, or for at least 30 days after the trial intervention, whichever comes first or until toxicity has resolved to baseline or ≤ Grade 1, or until the toxicity is considered to be irreversible. Perceived

lack of efficacy is not an AE. An exacerbation of a pre-existing condition is an AE.

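### The schedule prompts for adverse events only in the exercise arm at weeks 8 and 16, whereas section 12 covers every participant throughout participation

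*Combined protocol and SAP*

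**What the plan says.** Section 9.4 lists "Record adverse events" as the last row of the intervention-arm block, marked at weeks 8 and 16 only. The standard-care block lists clinical and activity updates, questionnaires, fitness tests and CT review, but no adverse-event (AE) row.

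Other sections are wider:

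- Section 12: "All Adverse Events will be reported directly to the sponsor".
- Section 12.1: "An adverse event is any untoward medical occurrence that the patient experiences whilst participating in the clinical trial". It adds that the event need not be related to the intervention.
- Section 12.4: "AEs must be recorded as they are reported during the visit". It asks for nature, dates, severity, relationship and outcome.
- Section 11: "Trial participation will cease once the final patient has completed their 26-week follow-up".
- Section 5.2, third objective: "To determine safety and tolerability of the exercise intervention and study assessments".

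Two further passages bear on the point. Section 12.3 says "Related SAEs will be any SAE that is reported as possibly, probably or definitely related to the prescribed exercise programme". Section 10 says "Total recruitment, recruitment rate, study drop-out rate and intervention adherence rate will be reported by simple descriptive statistics" (or proportions where appropriate) and does not mention AEs, although the synopsis lists them as secondary outcome 6.

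**The concern.** A site that follows the schedule would prompt for AEs in one arm and stop at week 16. A site that follows section 12 would record them in both arms to week 26. Both could claim to comply, yet they would hold different data.

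Under the schedule, exercise-arm events are elicited, while standard-care events depend on what patients volunteer and on the clinical updates. AE proportions would then not be like-for-like. The problem is greatest for the events that section 12.5.1 expects to be common (fatigue, muscle soreness, joint pain, musculoskeletal injury), because these need not lead to an admission or a treatment change. Section 4.1 names fatigue as a frequent symptom of the disease itself, so an exercise-arm fatigue rate is hard to interpret without the background rate in standard care. Section 9.1 also leaves standard-care patients free to exercise, so exercise-type events can occur there too.

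The study-assessment half of objective 3 is only partly served. A serious event caused by a fitness test would still be an SAE under section 12.2, but section 12.3 gives it no related category.

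**Working it through.** The plan states no figure on this point, so there is none to reproduce. The check is a row-by-row reading of section 9.4 against the other sections, followed by timing arithmetic.

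**1. Is the row really for one arm?** Questionnaires, fitness tests, CT review and clinical updates apply to both arms and are printed separately in each block. The AE row is printed in one block only, so it reads as exercise-arm only.

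**2. Visits covered.** After randomisation there are 3 visits (weeks 8, 16, 26) × 2 arms = 6 arm-visits. Marked: 2, made up of 2 of 3 in the exercise arm and 0 of 3 in standard care. If baseline is included for both groups, the count is 4 × 2 = 8 cells with 2 marked. Baseline precedes randomisation, so 2 of 6 is the cleaner figure.

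**3. Fitness tests covered.** Sections 7, 9.1 and 9.2 give tests at baseline and week 16 for both groups: 2 × 2 = 4 group-by-session occasions. One coincides with a scheduled AE record (exercise arm, week 16).

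**4. Time covered in the exercise arm.** Week 26 is day 182 and week 16 is day 112. 182 − 112 = 70 days, and 70/182 = 38%.

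**5. Share of planned follow-up.** Assume 40 patients split 20/20, all followed to week 26. The total is 2 × 20 × 26 = 1,040 patient-weeks.

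| Week-16 visit held at | Patient-weeks spanned | Share |
|---|---|---|
| week 13 (earliest in window) | 20 × 13 = 260 | 25.0% |
| week 16 (nominal) | 20 × 16 = 320 | 30.8% |
| week 19 (latest in window) | 20 × 19 = 380 | 36.5% |

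These are shares of planned follow-up, not estimates of lost events.

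**6. Does the 30-day rule in section 12.4 explain the week-16 stop?** Taking week 1 as day 7, a start within ±7 days is day 0 to 14. Adding 84 days, the 12-week programme ends on day 84 to 98 (nominally day 91). Thirty days later is day 114 to 128 (nominally day 121). All these dates fall after the nominal week-16 visit on day 112, although that visit's window runs from day 91 to day 133. The rule also governs how long a recorded event is followed, not when events are first recorded. It does not account for the stop.

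**7. Edge case.** With the latest permitted start (day 14) the programme ends on day 98. A week-16 visit held on days 91 to 97, which the window allows, would place the last scheduled AE record before the programme ends. This needs both a late start and an early visit.

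**The case against.** The strongest reply is that section 12 still binds where the schedule is silent. All AEs must be recorded, both arms have contacts at weeks 8, 16 and 26, and clinical updates there capture admissions and treatment changes. Interviews also ask about the fitness assessments. On this view the gap is a missing prompt. That is a fair description of the gap, but it does not remove it. Section 12.4 records what is reported at a visit without requiring anyone to ask, and the updates in sections 9.1 and 9.2 do not specify the severity, relatedness, dates and outcome that section 12.4 wants.

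Other points carry some weight:

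- The 30-day clause suggests section 12 is partly centred on the intervention, so the exercise-only row may be deliberate. If so, the other sections need to say so.
- Equal prompts would not fully equalise ascertainment, because the exercise arm also has a weekly supported session for 12 weeks and a route for raising clinical concerns. This limits what the fix achieves but does not justify prompting one arm only.
- The patient-week shares assume full recruitment and no death or drop-out. They show scale only.
- Section 10 also leaves out the ineligibility proportion and the questionnaire completion rate, so its silence is not specific to AEs. It is a lesser point, and the inconsistency does not rest on it.
- The table was read from a PDF, so a lost common-row boundary cannot be wholly excluded. Such a boundary would not supply the missing baseline and week-26 marks.

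**Conclusion.** The concern holds and should be fixed. Section 9.4 is inconsistent with sections 12, 12.1 and 12.4 on who has AEs recorded and for how long, and it only partly serves the study-assessment half of objective 3. Scheduled recording covers 2 of 6 post-randomisation arm-visits and coincides with 1 of 4 fitness-test occasions. It leaves the last 38% of nominal exercise-arm follow-up without a scheduled record. The visit counts depend on reading the AE row as exercise-arm only, and the 38% depends on nominal visit dates.

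The consequence is limited to a descriptive secondary outcome. The progression criteria in section 13 use recruitment and adherence only, and no between-arm AE comparison is planned.

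**What to change.** Reconcile section 9.4 with sections 5.2, 12.1 and 12.4:

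- Make AE recording a single row common to both arms, at baseline (after the fitness tests) and at weeks 8, 16 and 26, using the same short prompt.
- Extend section 12.3 so that relatedness is judged against the exercise programme or a study assessment.
- State in section 10 that the number and proportion of patients with any AE, any SAE and any related event will be summarised descriptively by arm.

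If recording in the exercise arm to week 16 is what is intended, say so in sections 5.2, 12.1 and 12.4, and state that AE rates will not be compared between arms.

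The cost is wording in three places. All patients attend baseline and both arms already have clinical updates at weeks 8, 16 and 26, so no visit is added. The downside is a few more minutes of CRF work per contact and more background disease events to log and report to the sponsor.
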